3.7.2.4 Management of Left Ventricular Ejection Fraction Decreased [PLD Cohort]

If a subject's left ventricular ejection fraction (LVEF) drops below institutional limit of normal or by at least 15% (absolute percentage points) from baseline value, study treatment (SL-172154, PLD or combination) should be discontinued. LVEF should be re-assessed within 45 days and every three months until full recovery. Upon full recovery, defined as LVEF increase to within 5% (absolute percentage points) of baseline within 45 days from LVEF nadir, study treatment (SL-172154, PLD or combination) can be resumed at investigator's discretion. Continuation of treatment should be followed by additional LVEF evaluation within 2 weeks.

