- Hormonal therapy will be counted as a separate line of therapy unless it was given as maintenance.

9. **[MIRV Cohort]** Willing to provide an archival tumor tissue block or slides or undergo procedure to obtain new biopsy using a low-risk, medically routine procedure for IHC confirmation of FR α positivity.

10. **[MIRV Cohort]** Subject's tumor must be positive for FR α expression defined as PS2+ \geq 25% by the Ventana FOLR1 Assay.

11. Eastern Cooperative Oncology Group Performance Status (ECOG PS) of 0 or 1.

12. Measurable disease by RECIST v1.1 using radiologic assessment.

13. Laboratory values must meet the following criteria:

Laboratory parameter	Threshold value
Absolute neutrophil count (ANC)	$\geq 1.5 \times 10^9/L$ without GCSF in prior 10 days or long-acting WBC growth factors in prior 20 days
Platelet count	$\geq 100 \times 10^9/L$ without platelet transfusion in prior 10 days
Hemoglobin (Hgb)	$\geq 9.0 \text{ g/dL}$ without packed RBC transfusion in the prior 7 days
Creatinine clearance (CrCl)	$\geq 30 \text{ milliliter (mL)/min}$ (using modified Cockcroft-Gault formula)
ALT/AST	$\leq 3 \times \text{ULN}$
Total bilirubin	$\leq 1.5 \times \text{ULN}$; subjects with isolated indirect hyperbilirubinemia are permitted if direct bilirubin ratio is < 35% and total bilirubin is $\leq 3.0 \times \text{ULN}$
Serum albumin [MIRV cohort only]	$\geq 2 \text{ g/dL}$
Left ventricular ejection fraction (LVEF) [PLD cohort only]	> 50% by echocardiography/MUGA scan

14. Females of childbearing potential (FCBP) must have a negative serum or urine pregnancy test within 4 days of the first dose of study treatment. FCBP must use 2 highly effective methods of contraception starting at least 14 days prior to the first dose of study treatment, throughout the study, and for at least 6 months after the last dose of PLD or at least 3 months after the last dose of SL-172154 or MIRV, or for the duration required by local regulatory guidance, whichever is longer.

15. Subjects must have stabilized or recovered (Grade 1 or baseline) from all prior anti-cancer therapy-related toxicities. NOTE: Grade 2 alopecia is acceptable for either cohort; Grade 2 sensory neuropathy **[PLD Cohort only]** or Grade 1 sensory neuropathy **[MIRV Cohort only]** is acceptable.

16. **[MIRV Cohort only, Dose Expansion only]** Willing to consent to 1 mandatory pretreatment and 1 on-treatment tumor biopsy, unless there is excessive risk from the procedure as determined by the investigator.

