3.7 Toxicity Management Guidelines

All AEs should be assessed using NCI-CTCAE v5.0 criteria. CRS will be graded per the ASTCT Consensus Grading Criteria for CRS (described in Section 3.7.1.2). Ocular AEs for MIRV will be graded per the tables in Appendix Section 16.6. These guidelines are not meant to be prescriptive, and investigators should always use clinical judgement. Investigators should always err on the side of caution if treatment-related toxicity is suspected. Subjects should be thoroughly evaluated to rule out any alternative etiology (e.g., disease progression, concomitant medications, and infections). In the absence of a clear alternative etiology, the possibility of an immune-related AE should be considered.

Every effort should be made to administer study treatment on the planned dose and schedule. If PLD or MIRV dosing is delayed, SL-172154 should also be delayed so that the dosing interval between PLD or MIRV and SL-172154 can be preserved. This will result in the cycle being delayed. If an SL-172154 dose is not given, the dose should be considered skipped, and the cycle should not be delayed. Please consult with the Medical Monitor if further guidance is needed.

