3.7.2 Toxicity Management Guidelines for PLD

The toxicity management guidelines provided in this section represent general guidance for AEs that are considered by the investigator to be possibly related or related to treatment with PLD. Dose modifications/interruptions or delays and treatment discontinuation of PLD for toxicity management should comply with local institutional guidelines or the current regional prescribing information for management of AEs related to PLD. If the country-specific prescribing information is more conservative, the current local guidelines should be used including the special precautions for patients who reach lifetime maximums of 450 mg/m².

In the event of significant toxicity, PLD dosing may be delayed and/or dose reduced as described below. In the event of multiple toxicities, dose modification should be based on the worst toxicity observed. **Table 5** describes the dose reductions to be used for AEs that are considered by the investigator to be possibly related or related to treatment with PLD.

Table 5 PLD Dose Reduction for Management of Toxicities

Dose Level	Dose Level Reduction (mg/kg)
Starting Dose	40 mg/m ²
First Dose Reduction	30 mg/m ²
Second Dose Reduction	20 mg/m ²

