NOTE: Progression should be calculated from the date of the last administered dose of platinum therapy to the date of the radiographic imaging showing progression.

NOTE: Subjects who are platinum refractory during front-line treatment are excluded [primary platinum-refractory disease, defined as disease that did not respond to (CR or PR) or has progressed within \leq 3 months of the last dose of first-line platinum-containing chemotherapy].

8. **[MIRV Cohort]** Subjects must have received at least 1 but no more than 3 prior systemic lines of anticancer therapy.

Lines of therapy are defined in this study as:

- Adjuvant \pm neoadjuvant is considered 1 line of therapy.
- Maintenance therapy (e.g., bevacizumab, PARP inhibitors) will be considered part of the preceding line of therapy (i.e., not counted independently).
- Therapy changed due to toxicity in the absence of progression will be considered part of the same line (i.e., not counted independently).
- Hormonal therapy will be counted as a separate line of therapy unless it was given as maintenance.

9. **[MIRV Cohort]** Willing to provide an archival tumor tissue block or slides or undergo new biopsy using a low-risk, medically routine procedure for IHC confirmation of FR α positivity.

10. **[MIRV Cohort]** Subject's tumor must be positive for FR α expression defined as PS2+ \geq 25% by the Ventana FOLR1 Assay.

11. Eastern Cooperative Oncology Group Performance Status (ECOG PS) of 0 or 1.

12. Measurable disease by RECIST v1.1 using radiologic assessment.

13. Laboratory values must meet the following criteria.

Laboratory parameter	Threshold value
Absolute neutrophil count (ANC)	$\geq 1.5 \times 10^9/L$ without GCSF in prior 10 days or long-acting WBC growth factors in prior 20 days
Platelet count	$\geq 100 \times 10^9/L$ without platelet transfusion in prior 10 days
Hemoglobin (Hgb)	$> 9.0 \text{ g/dL}$ without packed RBC transfusion in the prior 7 days
Creatinine clearance (CrCl)	$\geq 30 \text{ mL/min}$ (using modified Cockcroft-Gault formula; Appendix Section 16.3)
ALT/AST	$\leq 3 \times \text{ULN}$
Total bilirubin	$\leq 1.5 \times \text{ULN}$; subjects with isolated indirect hyperbilirubinemia are permitted if direct bilirubin ratio is $< 35\%$ and total bilirubin is $\leq 3.0 \times \text{ULN}$
Serum albumin [MIRV cohort only]	$\geq 2 \text{ g/dL}$
Left ventricular ejection fraction (LVEF) [PLD Cohort only]	$> 50\%$ by ECHO/MUGA

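### The PLD restart test for LVEF omits the institutional limit of normal that stops treatment, so a subject whose baseline is less than 5 points above that limit can qualify to restart while still below it (minor)

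*Protocol*

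**What the plan says.** Protocol Section 3.7.2.4 has two stopping triggers. Study treatment is to be discontinued if LVEF "drops below institutional limit of normal or by at least 15% (absolute percentage points) from baseline value". Treatment may resume after full recovery, a term the paragraph defines for itself: "defined as LVEF increase to within 5% (absolute percentage points) of baseline within 45 days from LVEF nadir". Resumption is permissive, since treatment "can be resumed at investigator's discretion", and it is followed by a check: "Continuation of treatment should be followed by additional LVEF evaluation within 2 weeks".

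Inclusion criterion 13, in the synopsis and in Section 4.1, sets the PLD cohort's entry LVEF at "> 50% by echocardiography/MUGA scan". Neither place ties entry to the institutional limit.

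Two general provisions sit above the paragraph. Section 3.7 says: "These guidelines are not meant to be prescriptive, and investigators should always use clinical judgement". Section 3.7.2 says that PLD dose changes and discontinuation "should comply with local institutional guidelines or the current regional prescribing information for management of AEs related to PLD", and lets more conservative country-specific information take over. Section 3.7.2 mentions the lifetime anthracycline maximum but gives no LVEF floor for restart.

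**The concern.** One stopping trigger is absolute (the limit) and the other is relative to baseline (15 points). The restart test is relative only. For a subject with a baseline close to the limit, one LVEF value can therefore be both a reason to stop and a value that counts as recovered. Because full recovery is explicitly defined, a reader cannot assume that it also means a return to the normal range.

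The drug concerned is an anthracycline. Section 1.7.1 notes that doxorubicin can damage the myocardium, up to acute left ventricular failure. The recheck comes after treatment continues, so a PLD dose may already have been given below the limit. The paragraph also does not say what to do if the recheck shows an unchanged value that is still below the limit. By contrast, Section 3.7.2.1 sets absolute floors for resuming PLD after cytopenia: ANC 1.5 and platelets 75 x 10^9/L.

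**Working it through.** The plan gives no figure to reproduce, so this is a check of the rule's logic.

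**Inputs**
- B = baseline LVEF. Eligible if above 50, so B is at least 51 in whole numbers (inclusion criterion 13).
- L = institutional limit of normal. The documents do not state it, so it is assumed over a range.
- x = LVEF when restart is considered.
- Stop if x < L, or if B - x >= 15 (Section 3.7.2.4).
- Restart test: x >= B - 5 within 45 days of nadir (Section 3.7.2.4), reading within 5 points as inclusive.

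**Limit trigger.** A subject can drop below the limit only from B >= L. Passing the restart test while still below the limit needs B - 5 <= x < L. Such an x exists exactly when B - 5 < L, that is, B - L < 5. In whole numbers the affected baselines are L <= B <= L + 4, and the band of x runs from B - 5 to L - 1, which is L - B + 5 values.

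| Assumed L | Eligible baselines affected | LVEF values that pass restart while below L |
|---|---|---|
| 46 or lower | none (would need B of 50 or less) | none |
| 47 | 51 | 46 |
| 48 | 51-52 | 46-47 (B = 51); 47 (B = 52) |
| 50 | 51-54 | 46-49 (51); 47-49 (52); 48-49 (53); 49 (54) |
| 53 | 53-57 | from 48-52 (53) down to 52 only (57) |
| 55 | 55-59 | from 50-54 (55) down to 54 only (59) |

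**Example, L = 50.** Baseline 52, nadir 45. The fall is 52 - 45 = 7 points, below 15, so only the limit trigger applies (45 < 50). Recovery to 48 leaves a gap of 52 - 48 = 4 points, which meets full recovery, yet 48 < 50. The example also holds if within 5 points is read as strictly less than 5.

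**15-point trigger.** B - x >= 15 and B - x <= 5 cannot both hold, so this trigger and the restart test do not overlap.

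**Exposure before the recheck.** PLD is given on Day 1 of a 28-day cycle (Section 5.2) and the recheck is due within 14 days of continuing. As 14 < 28, normally at most one PLD dose precedes it.

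**Population.** 12 in escalation plus 14 in expansion gives about 26 PLD subjects (Section 3.1.1). The documents give no distribution of baseline LVEF, so the affected number cannot be calculated.

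**With the limit added.** Requiring x >= L as well as x >= B - 5 leaves no qualifying value below L for any B >= L.

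**The case against.** The strongest reply is that the paragraph should be read as a whole. Its first sentence still tells the investigator to stop below the limit. The restart sentence only permits, and Section 3.7 asks investigators to lean towards caution when treatment-related toxicity is suspected. An investigator facing an LVEF of 48 with a limit of 50 therefore has a stated reason not to restart. Local PLD guidance or prescribing information may also be stricter, the recheck limits exposure, and the investigator may resume SL-172154 alone. Judging recovery against the subject's own baseline is also a coherent clinical choice.

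Most of this stands, and it settles the size of the point. A reader might infer that the protocol directs treatment below the limit, or allows repeated PLD dosing there. The documents do not support either reading: restart is discretionary, and the recheck normally falls before a second PLD dose, when the stopping rule can be applied again.

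The reply does not remove the inconsistency. Discretion operates after a definition that already calls the subject recovered. The outside guidance is not in the file, and nothing in the protocol makes the limit a condition of restart. If a purely baseline-relative recovery test was intended, the protocol does not explain why an absolute limit stops treatment but plays no part in restarting it.

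**Conclusion.** The point holds as a minor patient-safety clarification. It applies only to PLD subjects whose baseline is at or above the institutional limit and less than 5 points above it. The condition B - L < 5 follows from the text. Every specific LVEF value above depends on an assumed limit, and at 46 or lower no eligible subject is affected.

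To matter in practice, it needs a near-limit baseline, a fall below the limit, recovery within 45 days into a band of 1 to 5 points, local guidance that does not prevent restart, and an investigator who chooses to restart. The number of subjects is probably small. No endpoint or efficacy analysis is affected. At most, a subject classed as recovered could carry the low flag in the ECHO listing described in SAP Section 8.8.

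A reader might also extend the point to subjects who enter with a baseline already below their site's limit, which is possible where the limit is above 51. The text does not support that extension: such a subject cannot drop below a limit that baseline already fails to reach, and the paragraph does not address the case.

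**What to change.** In Section 3.7.2.4, define full recovery as LVEF within 5 percentage points of baseline within 45 days of nadir and, for subjects whose baseline was at or above the institutional limit of normal, also at or above that limit.

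Leave the stopping rule unchanged. In particular, do not add a provision that subjects with a baseline below the limit are governed only by the 15-point trigger. With an assumed limit of 55, a subject with baseline 55 would stop at 54, while one with baseline 54 would stop only at 54 - 15 = 39 and could restart at 54 - 5 = 49. The weaker protection would go to the subject with the lower starting LVEF.

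The cost is one added condition and no new assessments. A few near-limit subjects could not restart, and the condition would also cover restarting SL-172154 alone. For a subject whose baseline equals the limit, the 5-point tolerance disappears: LVEF must return to baseline within the 45 days.

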3.7.3 Toxicity Management Guidelines for MIRV

The toxicity management guidelines provided in this section represent general guidance for AEs that are considered by the investigator to be possibly related or related to treatment with MIRV.

3.7.3.1 MIRV Treatment Criteria

In the absence of an AE that requires dose modification (as specified in the management guidance for a particular toxicity), a subject must meet the following criteria to receive MIRV at any cycle:

- Absolute neutrophil count (ANC) must be $\geq 1.5 \times 10^9/L$ (1,500/ μ L)
- Platelet count must be $\geq 100 \times 10^9/L$ (100,000/ μ L)
- All non-hematologic toxicities for which a causal association to MIRV cannot be ruled out, must be \leq Grade 2 or returned to baseline; the exceptions to this rule being:
 - Treatment-emergent ocular disorders, which must have recovered to Grade < 1 or baseline
 - Treatment emergent pneumonitis which must have recovered to Grade ≤ 1

Dose reductions to be used for AEs that are considered by the investigator to be possibly related or related to treatment with MIRV are described in [Table 6](#).

Table 6 MIRV Dose Reduction Dose Levels

If the subject was receiving MIRV at:	Dose should be reduced to:
6.0 mg/kg AIBW	5.0 mg/kg AIBW
5.0 mg/kg AIBW	4.0 mg/kg AIBW
4.0 mg/kg AIBW	Permanently discontinue

Reduction of MIRV below 4.0 mg/kg will not be permitted. Dose re-escalation is not permitted.

Abbreviations: AIBW = adjusted ideal body weight; MIRV = mirvetuximab soravtansine

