3.7.3.5.1 Monitoring and Preventive Measures [MIRV Cohort]

In early dose escalation there was a relationship observed between MIRV plasma exposure and likelihood of an ocular event as well as with response. Exposure-response modeling suggested that a dose of 6.0 mg/kg AIBW provided adequate exposure for response while also maintaining overall exposure within a range that decreased the potential for ocular AEs. Due to the observation of ocular disorders consistent with reversible keratopathy/corneal epitheliopathy in subjects treated with MIRV, ocular function will be carefully monitored. Ocular symptom assessments will be performed at baseline and at Day 1 of every cycle thereafter (Section 6.2).

A complete ophthalmic examination will be performed in all subjects receiving MIRV by an ophthalmologist, optometrist, physician assistant, or equivalent eye care professional and will include the following at a minimum: manifest refraction, best distance corrected visual acuity (BCVA), intra-ocular pressure (IOP) assessment, fundoscopy, and slit lamp examination to assess the cornea for keratopathy and other corneal abnormalities. The visual acuity assessment should be performed with refraction, rather than corrected or via pin hole. Fundoscopy is required at baseline and post-treatment visit (PTV) only.

- A complete ophthalmic examination will be performed in all subjects receiving MIRV at baseline (within 21 days before C1D1), prior to Day 1 dosing in Cycles 3, 5, and 7 and at

the PTV (\pm 2 weeks) including subjects who are asymptomatic or have \leq Grade 1 ocular AEs. Abnormal corneal findings in asymptomatic subjects will be managed as per [Table 8](#).

- Subjects receiving MIRV who experience CTCAE $>$ Grade 1 ocular AEs while on study will have a complete ophthalmologic examination performed at the emergence of symptoms and at every other cycle thereafter until resolved to baseline or deemed irreversible in the opinion of the eye care professional. Subjects requiring an ophthalmological examination due to symptoms prior to Cycle 2 or 4 will then proceed to every other cycle (approximately 6 weeks) exams as indicated by findings and do not require the routine, asymptomatic exams at Cycle 3, 5, and 7.

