3.7.3.5.2 Management and Dose Modifications Guidelines [MIRV Cohort]

If a subject develops new CTCAE $>$ Grade 1 ocular symptoms, MIRV will be held until the subject undergoes a complete examination by an eye care professional. If a subject is found to have confluent superficial keratitis, a cornea epithelial defect, or a 3-line or more loss in BCVA, MIRV dosing must be interrupted until findings improve to nonconfluent keratitis, prior baseline, or complete resolution. Uveitis must improve to Grade 1 or better or prior baseline. Treatment with MIRV may resume if the ocular event improves as above within 28 days of the next scheduled MIRV dose (refer to [Table 8](#) and [Table 9](#) for details). Corneal AEs of any severity should be followed to complete resolution, pretreatment baseline, or are deemed to be irreversible according to the eye care professional. For 2 or more overlapping ocular adverse events (ocular disorders/corneal adverse reactions), dose modification should be based on the ocular adverse event of greater severity. Any other ocular AEs not specifically noted in [Table 8](#) or [Table 9](#) will be managed at the discretion of the treating physician in consultation with their eye care professional.

Subsequent eye examinations will be scheduled to occur in every other cycle going forward from the time that the corneal AE was initially reported until resolution of the corneal toxicity to subject's prior baseline or complete resolution or until it is deemed irreversible even if the results of the subject's ocular symptom assessment show no obvious clinical findings. For subjects with ongoing keratitis/keratopathy, a cornea epithelial defect, or a 3-line or more loss in BCVA at the PTV, an ophthalmic examination should be done every 30 days until complete resolution, stabilization without likelihood of improvement in the opinion of the eye care professional, or return to pretreatment baseline. Ocular symptoms (e.g., blurred vision) should also be assessed at this time. The visual acuity assessment should be performed with refraction, rather than corrected or via pin hole. Refraction is crucial for cases where subjects report blurred vision or other ocular AEs.

Management of ocular AEs with inflammatory characteristics or other non-corneal/visual acuity ocular AEs should include measures as indicated by an eye care professional.

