Corneal ulcer or clinically significant stromal opacity or BCVA 20/200 or worse	Complete eye examination as outlined in SOA (Section 6.2). Subjects should have weekly symptomatic ocular assessments and repeat eye examinations at least	Hold MIRV dosing. Subjects may be allowed to resume MIRV at one lower dose level after AE has resolved to

Ocular Exam Finding ^a	Management	Guidelines for MIRV Dose Modification
	every 6 weeks until resolved to baseline or are deemed to be irreversible by the investigator, even after treatment discontinuation, if needed.	nonconfluent keratitis or better or to pretreatment baseline within 28 days. If findings persist >28 days, continuation at reduced dose level is at the discretion of the investigator in consultation with the Sponsor.
Corneal perforation	Complete eye examination as outlined in SOA (Section 6.2). Subjects should have weekly symptomatic ocular assessments and repeat eye examinations at least every 6 weeks until resolved to baseline or are deemed to be irreversible by the investigator, even after treatment discontinuation, if needed.	Permanently discontinue MIRV dosing.

^a Normal = clear cornea, no epithelial defects.

^b Nonconfluent microcystic epithelial change, punctate epithelial keratopathy, subepithelial inclusion cyst and/or nonconfluent superficial keratitis, superficial punctate keratitis, epithelial erosion

Table 9 Management of Ocular Disorders

Refer to [Table 8](#) for Corneal Adverse Reactions.

Severity Grade (CTCAE v5.0)	Management	Guidelines for MIRV Dose Modifications
Grade 1	Follow SOA (Section 6.2) Monitor for worsening symptoms	Continue MIRV dosing
Grade 2	Complete eye exam as outlined in SOA (Section 6.2) Repeat complete exam as clinically indicated. Subjects should have weekly symptomatic ocular assessments by the investigator until the symptoms resolve to Grade \leq 1 or are deemed to be irreversible by the investigator.	Hold MIRV dosing until AE has resolved to Grade 1 or better. Subjects with ocular symptoms lasting < 14 days may be allowed to resume MIRV at the same dose level. Subjects with ocular symptoms lasting \geq 14 days but no more than 28 days may resume MIRV at one lower dose level. Recurrence of Grade 2 toxicity on subsequent cycles despite best supportive care will require a MIRV dose reduction of one dose level.

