Grade 3	Complete eye exam as outlined in SOA (Section 6.2). Repeat complete exam as clinically indicated. Subjects should have weekly symptomatic ocular assessments by the investigator until the symptoms resolve	Hold MIRV dosing. Subjects may be allowed to resume MIRV at a lower dose after AE has resolved to Grade 1 or better within 28 days. Recurrence of Grade 3 toxicity on subsequent cycles despite best supportive care will require a MIRV dose reduction of one dose level.

Severity Grade (CTCAE v5.0)	Management	Guidelines for MIRV Dose Modifications
	to Grade \leq 1 or are deemed to be irreversible by the investigator.	
Grade 4	Complete eye exam as outlined in SOA (Section 6.2). Repeat complete exam as clinically indicated. Subjects should have weekly symptomatic ocular assessments by the investigator until the symptoms resolve to Grade \leq 1 or are deemed irreversible by the investigator.	Permanently discontinue MIRV.

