h.	
Physical Examination: A full physical exam is required only at screening and PTV. Physical exams should be performed per standard of care during the on-treatment period.

i.	
Vital Signs and Pulse Oximetry: Blood pressure (BP), heart rate (HR), temperature (T) and respiratory rate (RR) must be measured after the subject has been sitting for at least five minutes (min). Pulse oximetry will be collected to coincide with vital sign time points noted below.
 
1. Collect vital signs/pulse oximetry on Day 1 of every Cycle at Predose (within 60 min of starting the MIRV infusion); postinfusion vital signs should be collected as clinically indicated for potential infusion-related reaction.2. Collect vital signs/pulse oximetry during Cycle 1 on Day 8 and Day 15: Predose (within 60 min of starting the SL-172154 infusion), at the end of infusion (EOI; \pm 5 min) and then 0.5 hour [hr] (\pm 5 min), 2 hr (\pm 10 min), and 4 hr (\pm 10 min) after end of infusion (EOI) of SL-172154.3. Collect vital signs/pulse oximetry on Day 8 and Day 15 of Cycle 2 and in each subsequent cycle: Predose (within 60 min of starting the infusion) and at the end of infusion [EOI] (\pm 5 min) of SL-172154.4. For subjects experiencing any grade IRR, refer to Section 3.7.1.1 for schedule of vital signs that should be measured at time of the IRR event.
j.	
Ocular Symptom Assessment: will be performed by the treating physician or other qualified individual before the start of each cycle for all subjects. For subjects receiving MIRV reporting new CTCAE $>$ Grade 1 ocular symptoms, treatment will be held until the subject is evaluated by an eye care professional for a complete examination. Refer to Table 8 and Table 9 for additional details on management of ocular findings on study.

k.	
Pregnancy Test: A serum pregnancy test (beta-human chorionic gonadotropin [β-hCG]) or urine pregnancy test must be performed at screening for all FCBP within 4 days of the first dose of MIRV on Cycle 1 Day 1. Repeat this test every 6 weeks during study treatment (i.e., C3D1, C5D1, C7D1, etc.) and at PTV. Contraception should be continued for at least 3 months after the last dose of either SL-172154 or MIRV.

l.	
Hematology/ Clinical Chemistry/ Coagulation/ TSH/ Free T4/ Antiviral Testing: will be performed at local laboratories according to the laboratory's normal procedures. Required laboratory tests are provided in Section 6.5.9.

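### The MIRV treatment criteria require ocular events to be below Grade 1 before dosing, while Table 9 says to keep dosing at Grade 1 (minor; check the symbol in the source first)

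*Protocol*

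**What the plan says.** Section 3.7.3.1 (MIRV Treatment Criteria) opens with a condition and an obligation: "In the absence of an AE that requires dose modification (as specified in the management guidance for a particular toxicity), a subject must meet" the listed criteria to be given MIRV, and this applies at any cycle. Non-hematologic toxicities possibly caused by MIRV must be at Grade 2 or lower or back to baseline, with two stricter exceptions. The first is ocular: "Treatment-emergent ocular disorders, which must have recovered to Grade < 1 or baseline". The second is pneumonitis, which must be at Grade 1 or lower.

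Section 3.7.3.5.2 holds the ocular dosing rules. In Table 9 the Grade 1 row says "Continue MIRV dosing". The Grade 2 row says "Hold MIRV dosing until AE has resolved to Grade 1 or better", and the Grade 3 row says "Subjects may be allowed to resume MIRV at a lower dose after AE has resolved to Grade 1 or better within 28 days". The text above the tables adds "Uveitis must improve to Grade 1 or better or prior baseline", and holds MIRV pending an eye examination only for new symptoms above Grade 1. Footnote j of the schedule in Section 6.2 uses the same trigger: for new symptoms above Grade 1, "treatment will be held until the subject is evaluated by an eye care professional for a complete examination".

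**The concern.** A site assessing a subject before Day 1 of a cycle has two instructions for the same finding. A new Grade 1 ocular event fails the mandatory criterion in 3.7.3.1 and passes Table 9.

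The situation is easy to meet. Table 15 in Appendix 16.6 grades dry eye as Grade 1 when it is only an asymptomatic observation or is relieved by lubricants. Ocular symptoms are assessed before every cycle, so the question can recur. Section 3.7.3.5 reports that ocular events on MIRV were common and mostly below Grade 3: blurred vision 42% at any grade and 2% at Grade 3 or above, keratopathy 33% and 1%, dry eye 26% and 1%.

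Under Section 3.7 a delayed MIRV dose also delays SL-172154 and lengthens the cycle. Table 7, footnote a, ends treatment when retreatment criteria are not met within 21 days of a missed dose, unless the guidance for that toxicity says otherwise. Table 9 may supply that exception, but a site would have to infer it. A site that doses under Table 9 could also be recorded as deviating from 3.7.3.1, since Section 6 allows no waivers.

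**Working it through.** No arithmetic applies. The check is to run both rules on the same subject.

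**Rule A (3.7.3.1):** dose only if the current grade is below 1 or equals baseline. Grades are whole numbers, so below 1 means 0.

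**Rule B (Table 9):** at Grade 1 continue; at Grade 2 or 3 hold, then resume at Grade 1 or better; at Grade 4 stop permanently.

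| Baseline grade | Current grade | Rule A | Rule B | Agree? |
|---|---|---|---|---|
| 0 | 0 | dose | no event, dose | yes |
| 1 | 1 | dose (at baseline) | continue | yes |
| 0 | 1, new event | withhold | continue | **no** |
| 0 | 2 or 3 | set aside by the lead-in | hold | no conflict |
| 0 | 1, after Grade 2 or 3 | may be set aside by the lead-in | resume | arguable |

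**Does the lead-in rescue the third row?** It switches off the criteria only when an event requires a dose modification under its own guidance. Table 9 requires none at Grade 1, so the criteria apply and the subject fails them. The reference to baseline helps only subjects who already had the finding at entry.

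**The fifth row is not counted as a conflict.** The original Grade 2 or 3 event did require a modification, so that subject can be argued to fall outside 3.7.3.1. Table 8 continues dosing for nonconfluent keratitis, but it works from examination findings and not CTCAE grades, so it is not counted either. One direct conflict remains.

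**Which line was intended?** The evidence for Grade 1 is indirect but all points one way:
- The uveitis rule and the Grade 2 and Grade 3 rows of Table 9 treat Grade 1 as good enough.
- The hold-and-examine triggers in 3.7.3.5.2, 6.2 and 6.5.7 start above Grade 1.
- The eye examination before Day 1 dosing in Cycles 3, 5 and 7 (3.7.3.5.1) covers all subjects, "including subjects who are asymptomatic or have" ocular events of Grade 1 or lower.
- The neighbouring pneumonitis bullet allows Grade 1, and its own Table 10 agrees: continue at Grade 1, and hold Grade 2 until it is at Grade 1 or lower. The ocular bullet is the one that does not match its table.

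**After the change.** With less-than-or-equal in Rule A, a new Grade 1 event passes (1 ≤ 1). The third row then reads dose under both rules, and no other row changes for the worse.

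**The case against.** The strongest objection is that an error has not been shown. The finding rests on one symbol in text read from a PDF by a program. Comparison signs do vary between copies of the same criterion. The hemoglobin threshold is at least 9.0 g/dL in the synopsis and above 9.0 g/dL in Section 4.1. The MIRV primary-refractory definition has a less-than-or-equal sign before 3 months in Section 4.1 and none in the synopsis. Writing Grade 0 as Grade < 1 is also unusual. Part of this stands: the available text cannot settle what the source shows. Against a misreading, less-than-or-equal is rendered correctly twice in the same list.

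The second objection is that sites are already sent to the right place. Section 3.7.3.5.1 tells them to follow Tables 8 and 9 for ocular signs or symptoms, Section 3.7 says the guidelines are not prescriptive, and 3.7.3 describes its content as general guidance. This limits the practical harm and is a good reason to rate the point minor. It does not reconcile a criterion worded as an obligation with a table that says the reverse, and the bullet has no pointer to the tables.

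The third objection is that the supporting text is indirect. The Cycle 3, 5 and 7 examinations set timing and do not govern eligibility to dose, and the hold triggers do not set a retreatment grade. That is correct, and the conflict does not depend on them. They bear only on which side to correct.

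Finally, nothing in the documents shows a dose withheld for this reason, and the summaries of changes do not mention this threshold. That is weak evidence, but it points toward a small practical effect.

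**Conclusion.** As printed, Section 3.7.3.1 and the Grade 1 row of Table 9 give opposite instructions for a new Grade 1 ocular event in a subject with a Grade 0 baseline. Nothing in 3.7.3.1 resolves the difference. The point holds at minor severity, with medium confidence because it depends on the symbol being the same in the source document.

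The size is one bullet against one table row. The number of subjects cannot be derived, because the reported ocular rates do not separate Grade 1 from Grade 2. The literal error withholds drug. No added ocular risk is claimed, and no effect on any sample size, boundary or estimate.

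**What to change.** First confirm the symbol in the source document. If it is less-than-or-equal, no change is needed.

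If it is a strict less-than sign, reword the bullet so that treatment-emergent ocular disorders must have recovered to Grade ≤ 1 or baseline, except as specified in Tables 8 and 9. The cross-reference makes clear which text governs and covers the corneal findings that Table 8 does not grade by CTCAE.

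The cost is a one-line correction in the next amendment or a clarification memo, a route the sponsor has already used for the visual acuity method. It adds no procedure, visit or subject.
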